### **Actual cumulative dose**

Cumulative doses will be derived for each of the study drugs: midostaurin, daunorubicin and idarubicin.

The actual cumulative dose refers to the total actual dose administered, over the duration for which the patient is on study drug as documented in the dose administration eCRF.

For patients who did not take any study drug, the actual cumulative dose is by definition equal to zero.

The actual cumulative dose is the sum of the non-zero doses recorded over the study drug dosing periods. Rest periods are not included.

### **Actual dose intensity (DI)**

Dose intensity (DI) will be derived for each of the study drugs: midostaurin, daunorubicin and idarubicin.

DI for patients with non-zero duration of exposure is defined as follows:

$DI \text{ (dosing unit / unit of time)} = \text{Actual cumulative dose (dosing unit)} / \text{Duration of exposure (unit of time)}$ .

For example, DI (mg/day) = Actual cumulative dose (mg) / Duration of exposure (day)  
= 1300 mg / 14 days  
= 92.9 mg/day

For patients who did not take any study drug the DI is by definition equal to zero.

### **Study day**

The study day describes the relative day of the event related to the start date of midostaurin.

The reference start date is designated as **Study Day 1**. Study Day -1 is the day that precedes Day 1. Study Day 0 is not defined. Study day is not to be used in numerical computations, for example in calculating exposure.

The study day will be calculated as:

- The date of the event (visit date, onset date of an event, assessment date etc.) - reference start date + 1, if event is on or after the reference start date
- The date of the event (visit date, onset date of an event, assessment date etc.) - reference start date, if event precedes the reference start date

The reference start date for all assessments (adverse events (AEs), laboratory etc.) will be the start date of study treatment.

The study day will be displayed in the data listings. If an event starts before the reference start date, the study day displayed in the listing will be negative.

#### **2.1.2 Baseline**

Baseline is the result of an investigation describing the “true” uninfluenced state of the patient, defined as the period from the date of signing any informed consent document to the start date of midostaurin.

The last non-missing assessment, including unscheduled assessments on or before the first dose of midostaurin is defined as “baseline value” or “baseline assessment”. Assessments, specified to be collected post-dose on the first date of midostaurin are not considered for baseline.

Where electrocardiogram (ECG) replicates are provided, the average of the ECG parameters at that assessment will be used in the analyses.

If patients have no value as defined above, the baseline value will be missing.

#### **2.1.3 On-treatment assessment/event**

The definition of on-treatment is given below, depending on the context.

For safety summary tables (over the entire duration of the study) an on-treatment AE is defined as any AE reported in the following time interval (including the lower and upper limits):

- <date of first administration of midostaurin; date of last administration of study treatment + 30 days>

This corresponds to the definition of treatment-emergent AEs given in the protocol, i.e. AEs which are newly reported or worsening from baseline.

An on-treatment assessment is defined as any assessment performed after the date of first administration of midostaurin (except for assessments specified to be collected post-dose on that day), i.e. assessments performed in the following time interval (including the lower and upper limits):

- <date of first administration of midostaurin + 1; date of last administration of study treatment + 30 days>

For patients whose last date of study treatment is missing, on-treatment assessments/events include any assessment/event present in the database occurring after the start date of study treatment.

Listings will contain all data, flagging assessments/events outside of the on-treatment period where applicable.

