5. Whether medication or therapy was given (no concomitant medication/non-drug therapy, concomitant medication/non-drug therapy)
6. Whether it is serious, where a serious adverse event (SAE) is defined as in [Section 8.2.1](#) and which seriousness criteria have been met

If the event worsens the event should be reported a second time in the CRF noting the start date when the event worsens in toxicity. For grade 3 and 4 adverse events only, if improvement to a lower grade is determined a new entry for this event should be reported in the CRF noting the start date when the event improved from having been Grade 3 or Grade 4.

All adverse events should be treated appropriately. If a concomitant medication or non-drug therapy is given, this action should be recorded on the Adverse Event CRF.

Once an adverse event is detected, it should be followed until its resolution or until it is judged to be permanent, and assessment should be made at each visit (or more frequently, if necessary) of any changes in severity, the suspected relationship to the study treatment, the interventions required to treat it, and the outcome.

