10.5.3.2 Adverse events (AEs)

Summary tables for adverse events (AEs) will include only AEs that started or worsened during the on-treatment period, the **treatment-emergent** AEs.

The incidence of treatment-emergent adverse events (new or worsening from baseline) will be summarized by system organ class, preferred term, severity (based on CTCAE grades), type of AE, relation to study treatment, periods and regimens as specified above and overall. AEs with different starts dates in different periods will be counted within each period.

AEs leading to discontinuation, serious AEs (SAE) and non-SAEs during the on-treatment period will be tabulated by type of AE.

All deaths (on-treatment and post-treatment) reportable as SAEs and non-fatal SAEs will be listed by patient and tabulated by type of AE.

All AEs, deaths and SAEs (including those from the pre and post-treatment periods) will be listed and those collected during the pre-treatment and post-treatment period will be flagged.

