### **2.9.1 Adverse events (AEs)**

The AEs will be re-coded using the latest version of the medical dictionary for regulatory activities (MedDRA) at the time of the analysis.

AEs will be graded using the common toxicity criteria for adverse events (CTCAE) Version 4.03. AEs will be summarized by period and overall for the safety set. AEs tables will be provided by age category. AEs with different starts dates in different periods will be counted within each period. If a patient reported more than one AE with the same preferred term (PT), the AE with the greatest severity will be presented. If a patient reported more than one AE within the same primary system organ class (SOC), the patient will be counted only once with the greatest severity at the SOC level, where applicable. An AE with missing CTCAE grade will be included in the 'All grades' column of the summary tables.

In AE summaries, the primary SOC will be presented alphabetically and the PTs will be sorted within the primary SOC in descending frequency.

Summary tables will be provided for:

- Overview of AEs and age category
  - In-text table
- All AEs regardless of relationship to study treatment by primary system organ class (SOC), preferred term (PT) and maximum severity and age category
  - In-text table by SOC and maximum severity
  - In-text table by PT and maximum severity
- AEs suspected to be related to study treatment by SOC, PT and maximum severity and age category
  - In-text table by PT and maximum severity
- AEs leading to treatment discontinuation regardless of relationship to study treatment by SOC, PT and maximum severity and age category
  - In-text table by PT and maximum severity
- AEs leading to treatment reduction or interruption regardless of relationship to study treatment by SOC, PT and maximum severity and age category
  - In-text table by PT and maximum severity
- Serious AEs (SAEs) regardless of relationship to study treatment by SOC, PT and maximum severity and age category
  - In-text table by PT and maximum severity
- On-treatment deaths by SOC and PT and age category
  - In-text table by SOC and PT
  - All deaths by SOC, PT and age category
- \*Non-SAEs regardless of relationship to study treatment (threshold=5%) by SOC and PT
- \*On treatment deaths and SAEs by SOC and PT

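### The SAP's date-only rule for on-treatment AEs, read literally, tabulates entries that only record a Grade 3/4 event improving

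*SAP*

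**What the plan says.** *Data entry.* For Grade 3 and 4 events, Protocol 8.1.1 says that "if improvement to a lower grade is determined a new entry for this event should be reported in the CRF". That entry is dated at the improvement and not at onset; the site completes it "noting the start date when the event improved from having been Grade 3 or Grade 4". One event can therefore yield several records, each with its own start date and grade. The same section defines an AE as something that appears or gets worse, and sends conditions present at consent to Medical History.

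*Protocol definition.* Protocol 10.5.3.2 says that the AE summary tables "will include only AEs that started or worsened during the on-treatment period", and that "The incidence of treatment-emergent adverse events (new or worsening from baseline) will be summarized".

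*SAP selection rule.* For safety summary tables, SAP 2.1.3 says that "an on-treatment AE is defined as any AE reported in the following time interval (including the lower and upper limits". The interval is "date of first administration of midostaurin; date of last administration of study treatment + 30 days". The SAP then adds: "This corresponds to the definition of treatment-emergent AEs given in the protocol, i.e. AEs which are newly reported or worsening from baseline".

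*Period tables.* SAP 2.9.1 says that "AEs with different starts dates in different periods will be counted within each period". Protocol 10.5.3.2 contains the same sentence.

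**The concern.** Once the database holds improvement entries, the SAP interval and the protocol definition select different records. An entry that only documents recovery has a start date inside the window, so the interval takes it in. It is neither a new event nor a worsening, so the definition leaves it out. The SAP says that the two correspond and gives no step that would make them agree.

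Safety is the primary objective, and the primary endpoint is a set of AE proportions. Patients consent during the chemotherapy week and AEs are recorded from consent, so some Grade 3/4 chemotherapy toxicity can be on file before midostaurin starts. The error can only add counts. It moves resolving chemotherapy toxicity into the midostaurin on-treatment profile, or an induction event into the consolidation table. The trial has a single arm, so there is no control group in which the same inflation would appear.

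**Working it through.** 1. **The plan's own figure.** Protocol 10.8 and SAP 3 give a 95% chance of seeing at least one case of an AE with 1% incidence in 300 patients. 1 − (1 − 0.01)^300 = 0.9510, as stated, and all 18 cells of the table reproduce to four decimals. That figure is not in dispute and does not change. The plan gives no figure for improvement entries.

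2. **A case taken through the rules.** A patient consents on Day 3 of induction chemotherapy. A Grade 4 event starts on Day 6, midostaurin starts on Day 8, and the event improves to Grade 3 on Day 10.
   - Protocol 8.1.1: a second entry is opened, Grade 3, start Day 10.
   - SAP 2.1.3 interval: Day 10 lies inside, so the entry counts as an on-treatment Grade 3 AE in induction.
   - Protocol 10.5.3.2: the event began before midostaurin and its grade fell, so it does not count.

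   Likewise, a Grade 4 induction event that improves to Grade 2 after consolidation has begun gets an entry dated in consolidation. The start-date rule then counts it there.

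3. **Does another rule remove the entry?**
   - The greatest-severity rule in SAP 2.9.1 chooses among records already selected. It drops none that is the only one in the window.
   - The rule joining entries with a gap of at most one day (SAP 2.9.1) is stated for occurrence counts in the registry tables. It is silent on a block that begins before midostaurin.
   - SAP 2.1.2 defines baseline through assessments. No baseline AE grade is defined, so worsening from baseline cannot be tested as written.
   - SAP 2.6.1 and 2.6.3 refer to Section 2.8, which reads as not applicable.

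4. **Who is exposed before midostaurin.** Consent falls on Days 1 to 7 (Protocol 7.1.2) and midostaurin starts on Day 8, so the source is at most about 7 days. Only Grade 3/4 AEs that begin or worsen after consent qualify.

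5. **Size, under assumptions.** Let p be the true treatment-emergent rate of a term. Let q be the share of the remaining patients who have an improvement entry for it in the window. Then reported rate = p + (1 − p)q, and extra patients = 301(1 − p)q, with 301 enrolled (SAP 1). The documents give neither p nor q.

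| p | q = 1% | q = 3% | q = 10% |
|---|---|---|---|
| 5% | 6.0% (2.9 patients) | 7.9% (8.6) | 14.5% (28.6) |
| 20% | 20.8% (2.4) | 22.4% (7.2) | 28.0% (24.1) |
| 95% | 95.1% (0.2) | 95.2% (0.5) | 95.5% (1.5) |

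   For example, 0.05 + 0.95 × 0.01 = 0.0595 and 0.05 + 0.95 × 0.10 = 0.145. Period tables use only the patients who entered the period, so the percentages carry over but the patient counts are smaller.

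6. **Grade 3&4 proportion.** Only entries that land at Grade 3 add to it. With s the share of such entries, reported rate = p + (1 − p)qs. At p = 20%:
   - s = 0: 20.0%, no change.
   - q = 3%, s = 25%: 0.20 + 0.80 × 0.03 × 0.25 = 20.6% (1.8 patients).
   - q = 10%, s = 50%: 0.20 + 0.80 × 0.10 × 0.50 = 24.0% (12.0 patients).

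**The case against.** The strongest reply is that the intended meaning is clear. SAP 2.1.3 itself names new or worsening AEs, Protocol 8.1.1 does not treat an improvement as an AE, and SAP 4 declares no change to the protocol's analyses. Dataset derivations sit in a separate programming specification that is not among the documents. This stands as far as intent goes: a reader might infer that recoveries have in fact been miscounted, and the documents do not show that. It does not rescue the rule as written. The sentence asserts equivalence without filtering anything, and a fresh CRF line can itself be read as newly reported.

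The per-period sentence is also the protocol's own, so there the SAP follows the protocol and does not depart from it.

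Exposure is limited too. Uncontrolled illness, including uncontrolled infection, is an exclusion. Protocol 7.2.1 ties the start of consolidation to hematologic recovery, with investigator discretion for CRi. Significant acute toxicity must have resolved before maintenance. These points reduce the number of open Grade 3/4 events at each boundary, but not to zero.

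Finally, the study tests no hypothesis, and all AEs are listed with out-of-window records flagged. That lowers the stakes. It does not make a wrongly selected proportion correct, and an improvement entry dated inside the window would carry no such flag.

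**Conclusion.** The point holds as a defect in a stated rule. Taken literally, SAP 2.1.3 counts improvement-only entries dated on or after first midostaurin, contrary to Protocol 10.5.3.2, and the period rule does the same at later phase boundaries. Whether the programs behave this way cannot be told from the documents.

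The effect lies mainly in preferred-term and period tables. With q assumed at 1% to 10%, a true 5% rate is reported as about 6.0% to 14.5%, about 3 to 29 extra patients of 301.

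A reader might infer that the whole primary endpoint is inflated; the documents do not support that. Deaths are unaffected, and an improvement entry would not normally be the one that leads to discontinuation. SAE follow-up reports attach to the first report of the event, although that governs the SAE form and not the AE page. The any-AE proportion moves by at most about 2 patients if it is near 95%. The Grade 3&4 proportion rises only through Grade 4-to-3 entries in patients with no genuine on-treatment Grade 3/4 event.

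A reader might also apply a much larger share, such as 5% to 30% of all patients (15 to 90 of 301). Nothing in the documents anchors such a share, and a total spread over many terms is not a change in any one reported statistic.

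**What to change.** In SAP 2.1.3 and 2.9.1:

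- Link consecutive entries of one event: same patient, same preferred term, gap of at most one day, looking back into the pre-treatment period.
- Count a linked entry as treatment-emergent only if the event is new in the on-treatment window or its grade exceeds the grade held at first midostaurin. For period tables, compare with the grade held at the start of the period.
- Do not use the worst earlier grade as the comparator. An event at Grade 4 on Day 4, Grade 2 on Day 8 and Grade 4 again on midostaurin is a real worsening from baseline, and that comparator would drop it.
- Keep improvement-only entries for listings and event duration, outside the incidence tables.
- Correct the sentence that equates the date interval with the protocol definition.

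The cost is SAP wording and minor AE-dataset programming. Existing AE dates, terms and grades are enough. The latest SAP version already postdates database lock, so the change should be recorded as a documented derivation with its date and reason. AE percentages would be slightly lower wherever improvement entries had been counted.

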#### **2.1.4 Definition of months and years**

A month will be calculated as  $(365.25 / 12) = 30.4375$  days. If duration is to be reported in months, duration in days will be divided by 30.4375. If duration is to be reported in years, duration in days will be divided by 365.25.

#### **2.1.5 Time windows**

Time windows for assessments are based on protocol specified windows, see protocol Table 7-1.

If more than one assessment is done within the same time window, the assessment performed closest to the target date will be used. For two assessments within a time window are equidistant from the target date then the earlier of the two assessments will be used. If there are multiple assessments for the same date, then the worst case will be used.

For unplanned visits, will be classified as follows:

Assessment	Target day of assessment	Time Interval
Baseline	Date when visit = IND C1D8 (or Day1)	Last date $\leq$ date of IND C1D8
INDC1	Date when visit = IND C1D8	Date of IND C1D8 - 7 $\leq$ date $<$ date of IND C2D1
INDC2	Date when visit = IND C2D8	Date of IND C2D1 $\leq$ date $<$ date of CON C1D1
CONC1	Date when visit = CON C1D8	Date of CON C1D1 $\leq$ date $<$ date of CON C2D1
CONC2	Date when visit = CON C2D8	Date of CON C2D1 $\leq$ date $<$ date of CON C3D1
CONC3	Date when visit = CON C3D8	Date of CON C3D1 $\leq$ date $<$ date of CON C4D1
CONC4	Date when visit = CON C4D8	Date of CON C4D1 $\leq$ date $<$ date of MAIN C1D1
MAINC1	Date when visit = MAIN C1D1	Date of MAIN C1D1 $\leq$ date $<$ date of MAIN C2D1

...	...	...
MAINC12	Date when visit = MAIN C12D1	Date of MAIN C12D1 <= date <= date of last non-zero dose +30
End Of Treatment	Date when visitnum =399	Date when visitnum in (399, 399.001,399.002,...)

### **2.1.6 Definition of end of study**

The study will end around 18 to 25 months (mo) after LPFV depending on number of cycles and recovery durations (2mo induction + 2mo recovery + 4mo consolidation + 4mo recovery + 12mo maintenance + 1mo safety follow-up). Study treatment will be provided until disease progression, death, unacceptable toxicities, physician's decision, patient/guardian's decision, protocol deviation, study termination by sponsor, lost to follow-up, technical problems, pregnancy, patient withdrew consent or until the end of study, whichever event occurs first. All patients must have safety follow-up for 30 days, after the last dose of study treatment except if study consent was withdrawn.

### **2.1.7 Early study termination**

The study can be terminated at any time for any reason by Novartis. Should this be necessary, the patient should be seen as soon as possible and the same assessments should be performed as for a discontinued or withdrawn patient.

### **2.1.8 Chemotherapy group assignment**

Patients will be assigned to '7+3' or '5+2' chemotherapy groups considering the following rules of the first induction cycle:

- If cytarabine duration is  $\geq$  7 days, '7+3' group will be assigned, without considering the duration of daunorubicin/idarubicin.
- If cytarabine duration is  $<$  7 days, '5+2' group will be assigned, without considering the duration of daunorubicin/idarubicin.

## **2.2 Analysis sets**

### **2.2.1 All enrolled patients**

The 'All enrolled patients' set comprises all screened patients who are not screening failures.

### **2.2.2 Full analysis set**

The Full Analysis Set (FAS) comprises all patients who received at least one dose of midostaurin and have a documented FLT3 mutation (ITD or TKD).

### **2.2.3 Safety set**

The safety set comprises all patients who received at least one dose of midostaurin.

## **Screening failures**

Patients who sign an informed consent form but fail to start on midostaurin for any reason.

### **2.3 Subgroup analysis**

Safety and efficacy data will be reported for the following subgroups:

- Age [(i)  $\leq 60$  /  $> 60$  years old and/or (ii)  $\leq 60$  /  $> 60$  to  $\leq 70$  /  $> 70$  years old]
- Gender (female / male)
- Chemotherapy groups ('7+3' / '5+2')
- Type of induction drugs (Daunorubicin ( $< 60$  mg/m^2), daunorubicin ( $\geq 60$  mg/m^2) and Idarubicin)

### **2.4 Patient disposition, demographics and other baseline characteristics**

#### **2.4.1 Patient disposition**

Disposition data will be listed and summarized descriptively by screening and period (induction, consolidation and maintenance) for the FAS.

Summaries will also include the number of patients who did not receive any dose of study treatment, having received at least one dose of study treatment, treatment completed as per protocol criteria or treatment permanently discontinued with reason, as reported in the dose administration record eCRF pages.

Informed consent and inclusion/exclusion criteria data will be listed. Screening data for screen failure patients will be listed.

#### **2.4.2 Patient demographics and other baseline characteristics**

Demographic and other baseline data (e.g. medical history, diagnosis and extent of cancer, eastern cooperative oncology group (ECOG) performance status, FLT3 mutation status etc.) will be summarized descriptively or listed as appropriate for the FAS.

Age will also be categorized as:

- $\leq 60$ ,  $> 60$  years and/or
- $\leq 60$  /  $> 60$  to  $\leq 70$  /  $> 70$  years old.

Demographic data for screen failure patients will also be listed.

### **2.5 Treatments (study treatment, concomitant therapies, compliance)**

#### **2.5.1 Dosing regimen**

All patients on study will receive standard chemotherapy plus midostaurin.

The protocol treatment allows 1-2 cycles of standard induction therapy with cytarabine and daunorubicin (or idarubicin) and up to 4 cycles of cytarabine consolidation, with midostaurin

given sequentially during each cycle, and up to 12 cycles of maintenance therapy with single-agent midostaurin as given in [Figure 1-1](#).

**Table 2-1 Dose and treatment schedule – Induction**

Treatment	Dose, route and frequency (based on 28-day cycles)
Cytarabine (Ara-C) with anthracycline (Idarubicin or Daunorubicin) (7+3)	Ara-C:100-200 mg/m  /day by CIVI days 1-7 (168 hour infusion) Daunorubicin: 60-90 mg/m  /day by IV push on days 1-3 or Idarubicin: 12 mg/m  /day by IV push on days 1-3
Cytarabine with anthracycline (Idarubicin or Daunorubicin) (5+2)	Ara-C:100 mg/m  /day by CIVI days 1-5 Daunorubicin: 60 mg/m  /day by IV push on days 1-2 or Idarubicin: 12 mg/m  /day by IV push on days 1-2
Midostaurin	50 mg (two 25 mg capsules) twice a day by mouth on days 8-28

